5.3. Interim Analysis Plan

5.3.1. Interim Analysis for Efficacy

No interim analysis for efficacy will be performed for several reasons. This study is a non-therapeutic study with minimal risks to the study participants. Stopping enrollment to one of the intervention arms at an interim analysis would impact the ability to evaluate secondary endpoints for the study.

5.3.2. Interim Analysis for Futility

No interim analysis for futility will be performed. Both intervention arms are considered minimal risk to participants.

5.4. Demographics and Baseline Characteristics

Demographic and baseline characteristics will be summarized for all patients. Characteristics to be examined include: patient characteristics (age, sex, race/ethnicity, performance status, disease and disease risk, educational status, household income, as well as health literacy level); donor characteristics (donor type, HLA-match); and transplant characteristics (transplant type, conditioning). Characteristics will be recorded for all patients who enroll on the BMT CTN 1205 (ETRIC) study, irrespective of whether they subsequently consent for the parent BMT CTN protocol. Between groups comparisons will be performed for continuous variables via a Kruskal-Wallis test and for categorical variables, via the chi-square test. The study will also apply Mantel-Haenszel methods to account for stratification by center and protocol. We are not expecting that the strata effect will be strong enough to change our findings. However, if a Kruskal-Wallis and Mantel-Haenszel produce different conclusions the underlying assumptions will be investigated for each of the tests and proceed with a method more appropriate for a given situation.

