4. PATIENT REGISTRATION AND ENROLLMENT FOR RANDOMIZED STUDY

4.1. Approaching Patients, Eligibility Screening and Obtaining Consent

Subjects may be approached for enrollment on the ETRIC protocol once they have been identified as potential participants for the BMT CTN 1101 or 1301 studies. Note that the BMT CTN 0901 trial and BMT CTN 1203 trial were removed as parent trials due to their closure on April 18, 2014 and May 13, 2016, respectively, and no further patients will be enrolled from these studies. The following scenarios regarding eligibility/participation in the ETRIC study can occur (Figure 4-1):

Figure 4-1. Possible Scenarios for Patient Registration

- 1) Scenario 1: On patient assessment, he/she is not found to be eligible for the parent trial. In this case, the patient would not be approached for participation in the BMT CTN 1205 (ETRIC) randomized study. He/she will proceed with HCT or other treatments as recommended by his/her physician.
- 2) Scenario 2: On patient assessment, he/she is found to be potentially eligible for the parent trial. However, on approaching the patient for the study, he/she indicates no interest in participation or going through the consent process. He/she will proceed with HCT or other treatments as recommended by his/her physician.
- 3) Scenario 3: On patient assessment, he/she is found to be potentially eligible for the parent trial and is interested in proceeding with the consent process for the study. Once patient expresses interest in the parent study, he/she will be approached for participating in the

BMT CTN 1205 (ETRIC) study. In this case, patient declines participation in the BMT CTN 1205 (ETRIC) study, and he/she will proceed with the consent process for the parent trial using their standard consent form.

- 4) Scenario 4: On patient assessment, he/she is found to be potentially eligible for the parent trial and is interested in proceeding with the consent process for the study. Once patient expresses interest in the parent study, he/she will be approached for participating in the BMT CTN 1205 (ETRIC) study. In this case, patient agrees to participate in the BMT CTN 1205 (ETRIC) study. He/she will be randomized and will undergo consent discussions for the parent study using either the ETRIC or the standard consent forms.

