In case a patient consents to and is enrolled on the BMT CTN 1205 (ETRIC) study, and then subsequently is found to not meet the eligibility criteria for the parent study (prior to the consent discussion for the study), he/she will be removed from the BMT CTN 1205 (ETRIC) study (this situation would be similar to Scenario 1 above). No ETRIC assessments will be conducted for such patients.

Patients who agree to participate in the BMT CTN 1205 (ETRIC) study, and then go through the consent process for but decline participation in or are later found ineligible for the parent study, will continue on the BMT CTN 1205 (ETRIC) study. They will be asked to complete all the assessments for the BMT CTN 1205 (ETRIC) study even though they do not proceed onto the parent study.

Transplant physicians or other center staff will evaluate patient eligibility for enrollment for the BMT CTN 1205 (ETRIC) study. Eligibility criteria will be verified and ineligible patients will proceed off study and no further study procedures will be conducted. Eligible patients willing to potentially participate in the BMT CTN 1205 (ETRIC) study will have a thorough discussion about the protocol with an investigator, a sub-investigator, clinical research nurse, or research coordinator. If necessary, this discussion may take place by telephone. During the discussion, the purpose of the study and study procedures will be presented as objectively as possible, and the potential benefits and risks of participation will be explained. Patients will be registered through EMMES AdvantageEDCSM (Electronic Data Capture, an Internet-based data entry system).

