4.4.3. Timing of Study Assessments

For the BMT CTN 1205 (ETRIC) study, enrolled patients will complete assessments within 7 business days of consent discussion for the parent trial. These will include assessments for health literacy and assessments for study endpoints (comprehension, anxiety, satisfaction, information location). These assessments will be conducted irrespective of whether the patient participates (and signs consent) or declines participation (and does not sign consent) for the parent study.

There are two sets of assessments:

- *Coordinator administered assessments*: These include – (1) REALM (health literacy), (2) NVS (health literacy), (3) Modified DICCT (comprehension), and (4) assessment for information location. Preferably, these assessments should occur right after the consent discussion for the parent clinical trial. However, if that is not feasible, they could be completed in a separate visit within 7 business days.
- *Patient self-administered assessments*: These will include – (1) QuIC (comprehension), (2) STAI (anxiety), and (3) assessment for satisfaction with the consent process. Preferably, these assessments should occur right after the consent discussion for the parent study. However, if that is not feasible, patients can be allowed to take them home and complete and return them by mail to the transplant center within 7 business days.

All study assessments will be administered using paper-based forms. Table 4-4-3 shows the timing of the study assessments for this study and their relation to patient reported assessments for the parentstudies.

Table 4-4-3: Patient Reported Assessments in the BMT CTN 1205 and Parent Studies

| Study/Instrument | Administered by | # of items | Within 7 business days of post-consent* | Pre-HCT ¹ | 100 Days | 180 Days | 12 mos | 24 mos | Time required |
|-----------------------------|-----------------|------------|---|----------------------|----------|----------|--------|--------|---------------|
| 1205 | | | | | | | | | |
| Health Literacy | | | | | | | | | |
| - REALM | Coordinator | 11 | X | | | | | | 2 minutes |
| - NVS | Coordinator | 6 | X | | | | | | 3 minutes |
| Comprehension | | | | | | | | | |
| - QuIC (A and B) | Self | 30 | X | | | | | | 7 minutes |
| - Modified DICCT | Coordinator | 11 | X | | | | | | 5 minutes |
| Anxiety | | | | | | | | | |
| - STAI | Self | 40 | X | | | | | | 5 minutes |
| Satisfaction | | | | | | | | | |

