- The Rapid Estimate of Adult Literacy Revised (REALM-R, a health literacy measure) will be scored as described in (Bass et all, 2003): words “fat”, “flu”, and “pill” will not be scored.
- The New Vital Sign (a health literacy measure) will be scored as described in (Weiss et al, 2005)
- The State-Trait Anxiety Inventory (STAI) will be scores as described in its manual (Spielberger et al, 1983)

NCT02081248

- The Consent Form Satisfaction Survey will be summarized by its total score as the sum of responses to its seven Likert questions (0-4).
- The Deaconess Informed Consent Comprehension Test will be scored as described in (Miller et al, 1996). The total score ranges between 0-28.

Primary Endpoint and Data Analysis:

The primary endpoint of BMT CTB 1205 is the mean comprehension score on the Quality of Informed Consent (part A) instrument.

The primary analysis will be performed using all patients who completed the Quality of Informed Consent (Part A) and will be based on the two sample t-test or, if the t-test assumptions are violated, with Mann-Whitney test. The statistical significance will be declared if the P-values of a two-sided test <0.05 .

The following non-primary analyses will use all randomized patients with possible exclusion of clinical trials protocols with high missing data rates. Non-primary analysis will rely on linear regression models with multiple imputations to address missing data issues.

Analysis of interactions between the randomized assignment and (1) the trial protocol, (2) literacy level (REALM-R), (3) income, (4) age groups, (5) education level. The statistical significance of interactions will be declared at ALPHA 0.01 (Bonferroni adjustment for 5 tests). If the interaction test is significant then post-hoc comparisons between the ETRIC and standard consent groups will be performed for each level of a categorical variable.

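### Health literacy is listed as a baseline characteristic of every enrolled patient, but REALM and NVS are given only after randomisation and the consent discussion, so it is missing for early leavers and unknown at enrolment

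*Protocol*

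**What the plan says.** Protocol 5.4 (Demographics and Baseline Characteristics) includes "educational status, household income, as well as health literacy level" in its list of patient characteristics, and says of the list: "Characteristics will be recorded for all patients who enroll on the BMT CTN 1205 (ETRIC) study".

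The order of events is set in Protocol 4.1 and 4.2. A patient who agrees to 1205 is randomised first: "He/she will be randomized and will undergo consent discussions for the parent study using either the ETRIC or the standard consent forms". Protocol 4.4.3 then says that "enrolled patients will complete assessments within 7 business days of consent discussion for the parent trial", and adds: "These will include assessments for health literacy and assessments for study endpoints (comprehension, anxiety, satisfaction, information location". Table 4-4-3 gives REALM and NVS this one time point and no earlier one.

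Protocol 4.1 treats two groups of leavers differently. Patients found ineligible for the parent trial before the discussion are removed from 1205: "No ETRIC assessments will be conducted for such patients". Patients who go through the discussion and then decline, or are later found ineligible, stay on study: "They will be asked to complete all the assessments for the BMT CTN 1205 (ETRIC) study".

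In the SAP (Primary Endpoint and Data Analysis), the non-primary analyses use all randomised patients, apart from a possible exclusion of parent protocols with much missing data. They include "Analysis of interactions between the randomized assignment and (1) the trial protocol, (2) literacy level (REALM-R") among five interaction factors. NVS or REALM-R, whichever predicts better, is also a candidate covariate in the adjusted model. The missing-data paragraph bases the imputation model on information held at enrolment. The Table 1 shell has no literacy row. Table 3 has a missing row for REALM-R, and a footnote leaves the missing group out of the calculations.

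**The concern.** The statement in 5.4 and the schedule in 4.1 and 4.4.3 cannot both hold. A patient who leaves between randomisation and the consent discussion is enrolled and randomised but can have no literacy value. Such patients are foreseen: they are the example that Protocol 5.2 gives for its dropout allowance.

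Literacy is a central covariate in this trial. Protocol chapter 1 calls it a possible major determinant of whether patients understand consent forms, and 2.1.3 relies on randomisation to balance it. Three things are at stake:

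- Balance on literacy can be shown only among patients who were assessed, and no SAP table is set up to show it.
- If the imputation model is confined to enrolment-time information, as the SAP says, it omits literacy. The imputed QuIC Part A scores then carry no direct literacy effect, which tends to pull the estimated literacy effect and its interaction with arm towards zero.
- If literacy is put into the model anyway, it is itself incomplete, and the SAP does not say how its missing values are handled. For the literacy interaction, the Table 3 footnote drops these patients, which does not fit an analysis of all randomised patients.

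**Working it through.** **1. The order of events.**

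| Step | Source | Literacy known? |
|---|---|---|
| Verbal consent to 1205 | Protocol 4.3 | No |
| Randomisation | Protocol 4.1, 4.2 | No |
| Leaves before the discussion: removed, no assessments | Protocol 4.1 | Never |
| Parent-trial discussion with the assigned form | Protocol 4.1 | No |
| REALM and NVS, up to seven business days later | Protocol 4.4.3 | Yes, if attended |

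No row gives a literacy value at enrolment, and one row rules it out altogether.

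**2. The plan's own sample size** (Protocol 5.2), needed here only to size the dropout group.

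- Two-sample t-test, difference 4, SD 8, two-sided alpha 5%, power 80%: exact solution 63.8, so 64 per arm. Stated: 64.
- Mann-Whitney allowance: 64 × 1.15 = 73.6, so 74 per arm and 148 in total. Stated: 74 and 148.
- Dropout: 148 / (1 − 0.25) = 197.3, so 198. Stated: 198.

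All reproduce, and nothing in this point disputes them.

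**3. Patients who leave before the discussion.** The 25% allowance is 198 × 0.25 = 49.5, about 50 patients. Section 5.2 offers failure to reach the consent process only as an example of dropout, so 50 is what follows if the whole allowance is of that kind.

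**4. Patients without QuIC Part A.**

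- The SAP expects about two thirds to complete it: 198 × 1/3 = 66 without it.
- With the SAP's 64 completers per arm: 198 − 2 × 64 = 70 without it, and 70 / 198 = 35%.

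**5. Overlap of missing literacy and missing QuIC.** The two are collected by different routes (Protocol 4.4.3). REALM and NVS are given by the coordinator, preferably straight after the discussion. QuIC is self-completed and may be taken home and mailed back. A patient who does not return QuIC can therefore have REALM and NVS on file. The documents do not divide the 66 to 70, so the number of them who also lack literacy runs from a few to all. As an illustration, if about 50 left before the discussion, 66 − 50 = 16 to 70 − 50 = 20 would lack QuIC Part A but might have literacy.

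**The case against.** The strongest reply has five parts.

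- *The sentence in 5.4 is aimed at another group.* It goes on to say that it applies whether or not the patient later consents to the parent trial, and decliners are indeed scheduled for the literacy tests. The same list holds donor and transplant characteristics, so it is not strictly an enrolment-time list. This explains the wording but does not remove the conflict: the main clause covers everyone who enrols, and Protocol 5.5 keeps all randomised patients in the intention-to-treat analysis.
- *Missing data are already provided for.* Protocol 5.5 plans imputation above 10% missing, and the SAP adds multiple imputation and a tipping-point analysis. This stands for the outcome. Neither document says how missing literacy is treated in the SAP's models, and the SAP's stated imputation inputs predate its measurement.
- *A reader might infer that literacy is missing for exactly the patients who lack the primary outcome*, so that unequal loss of low-literacy patients could never be seen. The documents do not support this. Collection routes differ, and post-discussion decliners are still assessed, so for patients who merely fail to return QuIC the comparison may be possible. The early leavers in 5.2's examples go because of disease progression or ineligibility, which gives no reason to think that literacy drives their loss.
- *A reader might infer that literacy scores are altered by the form under test.* REALM is word recognition and NVS uses a nutrition label. Nothing in the documents suggests that reading either consent form changes these scores, or does so differently by arm.
- *Rescheduling comes too late and is incomplete.* Both parts stand. The SAP reports that enrolment closed in August 2016 with 198 patients. Consent to 1205 may be by telephone, and a telephone enrolee who never reaches the consent visit would still be untested.

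**Conclusion.** The inconsistency is real and limited. Literacy is a post-randomisation measurement, absent for patients who leave before the consent discussion and unavailable at enrolment for the imputation model. The protocol nevertheless describes it as a baseline characteristic of all enrolled patients, and the SAP uses it in analyses of all randomised patients.

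The size cannot be fixed from the documents. About 50 of 198 is a ceiling for early leavers and assumes that the whole 25% allowance leaves before the discussion. The 66 to 70 of 198 (33% to 35%) counts missing QuIC Part A, not missing literacy, and is reached for literacy only if every one of those patients also missed the coordinator tests.

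The primary comparison is unadjusted, so it and the sample size are untouched. What is affected is the literacy interaction, the adjusted model, the imputation and the description of completers against all randomised patients. The correction is cheap and worth making, but the trial's main result does not depend on it.

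**What to change.** **Design (a correction to the schedule; it can no longer recover data in this trial).** In Protocol 4.4.1, 4.4.3 and Table 4-4-3, place REALM and NVS after verbal consent to 1205 and before randomisation. For patients who consent to 1205 by telephone, give them at the start of the consent visit before either form is opened, accepting that anyone who never reaches that visit stays missing. The instruments, the coordinator and the total time do not change. The cost is 2 + 3 = 5 minutes before the consent discussion.

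**Analysis (still possible).** In the SAP:

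- Add literacy to Table 1 by arm with missing counts, and show it by QuIC Part A completion within arm.
- Label it as measured after randomisation.
- Include it in the imputation model where observed, impute it where missing, and amend the sentence that limits that model to enrolment-time information. Bring the Table 3 footnote into line with this.

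Reconcile the statement in Protocol 5.4 with 4.1 and 4.4.3, so that it says for whom literacy is actually available. The cost is two tabulations and a few sentences; no sample-size figure changes.

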5.5. Analysis Plan

The primary analysis will be performed using the intention-to-treat principle so that all randomized patients will be included in the analysis. The t-test or the Mann-Whitney test will be used if the t-test assumptions are violated. Secondary endpoints of subjective comprehension, anxiety, satisfaction, and information location will be analyzed with the Mann-Whitney test. The binary outcome of consent rates will be compared using the Fisher exact test. The above unadjusted analyses will be complemented by analyses that adjust for potentially confounding

variables in regression analyses. Generalized estimating equations (GEE)⁵⁰ will be used to control for effect of confounding variables (e.g., patient demographics, health literacy level, strata) and a potential consenter effect (as more than one clinician could be involved in the consent process at a clinical trial site). GEE with identity link will be used for comprehension, anxiety and satisfaction analyses. Information location will be analyzed with LOG link and LOGIT link with accrual outcome. Variance will be estimated with the sandwich estimator if the number of consenters is > 30; otherwise the “leave-one-consenter-out” jackknife variance estimation will be used.⁵¹ Exact logistic regression will be used with accrual if the problem of small counts appears. Otherwise Wald tests will be used for significance testing. All two-way interactions between the group indicator (ETRIC vs. standard) and confounding variables will be tested and added to the model if significant. It is expected that all confounders will be analyzed as fixed effects except for the consenter which will be the repeated factor in the GEE. The form of continuous predictors will be either linear, quadratic, or categorized depending on the number of clusters observed in the dataset. Every category in categorical variables will have at least 10 subjects otherwise we will consider merging with neighboring categories. The presence of missing data in excess of 10% will be addressed by developing an imputation model for missing components given the observed part. Then, the multiple imputations approach will be used to estimate regression parameters and their standard errors.⁵²

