5.2. Sample Size and Power Calculations

Based on previous studies in the literature,^{4,43,44} this study is designed to detect a 4-point difference in the mean QuIC part A comprehension scores between the two study arms. This difference represents a 0.5 standard deviation difference and has been considered to represent a clinically meaningful difference in comprehension scores in previous studies. The sample size for a two-sample t-test will require 64 participants per group to detect a 4-unit difference between group means ($\alpha=5\%$, power=80%, standard deviation=8). Asymptotic relative efficiency of the Mann-Whitney test to the 2-sample t-test is 0.864 under any symmetric

distribution, which means that 15% more subjects will need to be recruited, leading to 74 per group or 148 in total. Another 25% is added to account for possible dropouts (e.g., patients consent for this study, but are subsequently not able to participate in the consent process for the BMT CTN parent clinical trial [e.g., due to disease progression or determined ineligible to participate]). The study will need to enroll 198 subjects (approximately 99 in each arm). The stratified randomization will eliminate possible association between trial and center strata and consent group assignment, which potentially increases power properties.

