Age (years)			
Education Level			

 - Education Group 1 (N) - Education Group 2 (N) - Education Group 3 (N) - ... - Missing (N) 			

* P-values column will provide global interaction tests and P-values for post-hoc comparisons between the regression coefficients ETRIC and standard consent groups (Missing Data group will be excluded from calculations).

Table 4: Adjusted analysis of Quality of Informed Consent (part A) instrument

Table will report the results of a parsimonious regression model

	Regression coefficient (+/-SE)	P-value
(Model intercept)	Coef (SE)	
ETRIC	Coef (SE)	
Covariate 1		

 - Category 1 	Coef (SE)	

NCT02081248

- Category 2	Coef (SE)	
- ...		
- Reference Category	0 (-)	
Covariate 2		
- Category 1 of Covariate 2	coef (SE)	
- Category 2 of Covariate 2	coef (SE)	
- ...		
- Reference Category of Covariate 2	0 (-)	
...		

P-values column will provide global P-values and P-values of post-hoc comparisons between versus the reference category. Indicator of ETRIC will always be included in the regression model; inclusion of other variables will depend on their significance level (<0.05).

References:

1. Steven Joffe, E. Francis Cook, Paul D. Cleary, Jeffrey W. Clark, Jane C. Weeks Quality of Informed Consent: a New Measure of Understanding Among Research Subjects *Journal of the National Cancer Institute*, Vol. 93, No. 2, January 17, 2001
2. Roderick Little and Donald Rubin. Statistical Analysis of Missing Data, 2002, 2nd ed., Wiley
4. Spielberger, C. D., Gorsuch, R. L., Lushene, R., Vagg, P. R., & Jacobs, G. A. (1983). Manual for the State-Trait Anxiety Inventory. Palo Alto, CA: Consulting Psychologists Press.
7. Little R. and Rubin D, Statistical Analysis with Missing Data. 2nd ed, 2002, Wiley

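### Protocol 5.5 adds significant ETRIC-by-covariate interactions to the supportive adjusted models without fixing coding or the reported effect, and the SAP follows a different rule without saying that it replaces 5.5

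*Protocol*

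**What the plan says.** **Protocol 5.5 (Analysis Plan).** The primary comparison is an unadjusted t-test, or a Mann-Whitney test if the t-test assumptions fail. On the regression models the protocol says "The above unadjusted analyses will be complemented by analyses that adjust for potentially confounding" variables, so these are supporting analyses. They are GEE models with the consenter as the cluster. The covariates are given only by example: "confounding variables (e.g., patient demographics, health literacy level, strata"). The interaction rule is: "All two-way interactions between the group indicator (ETRIC vs. standard) and confounding variables will be tested and added to the model if significant". Apart from exact logistic regression for sparse consent data, "Otherwise Wald tests will be used for significance testing". Continuous covariates may be linear, quadratic or categorised.

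**SAP, Primary Endpoint and Data Analysis.** The primary test is the t-test or Mann-Whitney test: "The statistical significance will be declared if the P-values of a two-sided test <0.05". For QuIC Part A, five interactions with arm are named (parent protocol, REALM-R literacy, income, age group, education): "The statistical significance of interactions will be declared at ALPHA 0.01 (Bonferroni adjustment for 5 tests"). A significant one leads to arm comparisons within each level, reported in Table 3. The adjusted model (Table 4) is built separately, by forward selection at 5% from six candidates, all main effects. "Indicator of ETRIC will always be included in the regression model".

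**SAP, Secondary Endpoints and Final Analysis.** QuIC Part B, DICCT, state anxiety and satisfaction get t- or Mann-Whitney tests. Information location gets a generalized linear model. Consent gets a logit GEE with parent protocol as a fixed effect and site as the cluster. No interactions are listed for any of these.

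**The concern.** Once an arm-by-covariate product is in a model, the arm coefficient is no longer an overall effect. It is the effect where that covariate is zero: the reference category, or the zero point of an uncentred score. That coefficient is correlated with the interaction, and the rule admits an interaction only when its estimate is extreme. A chance interaction can therefore both change what the adjusted ETRIC effect means and push it towards significance, and nothing in 5.5 tells the analyst to report anything other than that coefficient.

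The two documents also give different adjusted models for QuIC Part A. For four secondary endpoints, 5.5 is the only text that describes a covariate-adjusted model, so its interaction rule applies there without a competing one.

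**Working it through.** **Plan's own figures.** Protocol 5.2 says "The sample size for a two-sample t-test will require 64 participants per group to detect a 4-unit difference", with SD 8, 80% power and 5% alpha. The exact t-test calculation gives 63.8, so 64 per group (power 0.801). Then 64/0.864 = 74.07, about 74 per group or 148 in total, and 148/0.75 = 197.3, so 198. These reproduce. Neither document states an error rate for the adjusted ETRIC coefficient.

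**Assumptions, because 5.5 is silent.** Interaction tests at 5%; 3 to 10 covariates; several codings; no true arm, covariate or interaction effect; 128 (2 × 64) or 198 patients.

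**Step 1: chance that at least one false interaction enters.** For k independent tests this is 1 − 0.95^k:

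| k | 3 | 5 | 6 | 8 | 10 |
|---|---|---|---|---|---|
| Chance | 14.3% | 22.6% | 26.5% | 33.7% | 40.1% |

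**Step 2: ETRIC coefficient given that an interaction has entered.** Take one binary covariate with a share r of patients at its reference level, and 1:1 arms. The variance of the ETRIC effect in the reference group is proportional to 1/r. The variance of the interaction (other group minus reference group) is proportional to 1/r + 1/(1−r) = 1/[r(1−r)]. Their covariance is proportional to −1/r. The correlation is therefore −√(1−r). Selecting the interaction at two-sided 5% and then testing the ETRIC coefficient at two-sided 5%, under bivariate normality, gives:

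| r | Correlation | P(ETRIC significant, given interaction selected) |
|---|---|---|
| 0.2 | −0.89 | 58% |
| 0.5 | −0.71 | 34% |
| 0.8 | −0.45 | 16% |

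**Step 3: combine, six binary covariates.** Rate ≈ P(selected) × conditional rate + P(none selected) × 5%:
- r = 0.5: 0.265 × 0.34 + 0.735 × 0.05 = 0.127
- r = 0.2: 0.265 × 0.58 + 0.735 × 0.05 = 0.190
- r = 0.8: 0.265 × 0.16 + 0.735 × 0.05 = 0.079

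**Step 4: simulation.** 3000 null trials per setting. Each interaction was tested one at a time with all main effects in the model, the significant ones were added, and the ETRIC coefficient was then tested at 5%. Ranges cover 128 and 198 patients.

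| Setting | Reference or uncentred coding | Centred |
|---|---|---|
| 3 balanced binary covariates | 9-10% | about 5% |
| 5 balanced | 11% | about 5% |
| 6 balanced | 12-13% | about 5% |
| 8 balanced | 15-16% | 4-6% |
| 10 balanced | 16-17% | 5-6% |
| 6 binary, reference level 80% of patients | 8-9% | not run |
| 6 binary, reference level 20% of patients | 19-20% | not run |
| 7-covariate mix, all categorical | 12% | 5-6% |
| Same mix, raw age and literacy | 15-16% | 5% |

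The simulation used ordinary least squares in place of the identity-link GEE, without consenter clustering or multiple imputation. It shows the mechanism and its order of size. It does not predict the trial's exact error rate.

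**SAP rule.** Because its interactions are tested apart from the Table 4 model, they cannot move the ETRIC coefficient there. The chance of at least one false interaction is 1 − 0.99^5 = 4.9%.

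**The case against.** Four points can be made in the plan's favour.

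- **The primary conclusion does not depend on this.** It rests on an unadjusted test, and the adjusted models only complement it. This stands in full. A reader might infer that the trial's type I error is inflated; the documents do not support that.
- **No single rate follows from the protocol.** A reader might take 12-17% as a property of 5.5. It is not: the interaction level, covariates, coding and reference groups are all unstated, and centring brings the rate back to about 5%. SAP Table 4 does show reference categories, but in a model whose candidates are all main effects. This stands, so only a conditional range can be given.
- **For QuIC Part A the SAP already has the better procedure.** It separates the interaction tests from the adjusted model. A reader might go on to apply the select-and-add inflation to the SAP's five tests at 0.01 (about 7% if those terms were added), but the SAP does not say they are added. What remains is that it never says it replaces 5.5.
- **Protocol 5.5 is not the only rule for every secondary endpoint.** The SAP sets its own models for consent and information location, without interactions. This stands for those two. It does not help QuIC Part B, DICCT, anxiety or satisfaction, for which the SAP gives only unadjusted two-sample tests. The SAP also plans no adjusted table for a secondary endpoint, so the practical reach may be small, but the protocol still promises those analyses.

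**Conclusion.** The concern holds for the supportive adjusted analyses. Protocol 5.5 states a data-driven rule that, under reference-level or uncentred coding, turns the ETRIC coefficient into a reference-group effect. Its false-positive rate is then roughly 8-20%, against about 5% for a main-effects or centred model. That range assumes 5% interaction tests, about 5 to 10 covariates, no true effects, and that the single ETRIC coefficient is the one reported. Six balanced binary covariates give about 12-13%.

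Separately, and without any assumption, the two documents conflict on QuIC Part A: one adds significant interactions to the adjusted model, and the other tests five of them apart from it at 0.01. Nothing says which prevails. For covariate-adjusted QuIC Part B, DICCT, anxiety and satisfaction, the 5.5 rule stands alone. This should be corrected before the adjusted results are produced, but it does not threaten the primary test.

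**What to change.** Replace the interaction sentence in Protocol 5.5, or override it explicitly in the SAP, so that:

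1. The adjusted ETRIC effect for every endpoint comes from a main-effects model.
2. Arm-by-covariate interactions are separate exploratory tests under the SAP's 0.01 rule and are not added to that model.
3. If an interaction is nevertheless retained in a model, covariates are centred and the ETRIC effect averaged over patients is reported.
4. The SAP rule is stated to govern QuIC Part A.

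The core change is one sentence, plus a line on precedence. It needs no new data or patients and reduces the modelling work.
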